Appendix A: Pharmacodynamic analysis

1 Montgomery and Asberg Depression Rating Scale (MADRS)

1.1 Introduction

The Montgomery–Asberg Depression Rating Scale (MADRS) consists of 10 items evaluating core symptoms of depression. Nine of the items are based upon patient report and one is on the rater's observation during the rating interview. Items are rated between 0-6 (0=no abnormality, 6=severe).

1.2 Analysis and reporting

The total score is calculated by adding the scores from the 10 items. The overall score ranges from 0 to 60. Higher scores suggest greater levels of depression. Total scores will not be calculated where there is a missing data. The individual questions will also be reported.

2 Mystical Experience Questionnaire (MEQ-30)

2.1 Introduction

The Mystical Experience Questionnaire (MEQ-30) was developed by Pahnkein 1963 as a tool for the evaluation of single mystical experiences occasioned by hallucinogens.

The MEQ-30 consists of 30 scale items (0- none/not at all to 5- extreme (more than any other time in my life and stronger than 4).

2.2 Analysis and reporting

Factor scores are computed by calculating the mean response to the following items:

- Mystical items are: 4, 5, 6, 9, 14, 15, 16, 18, 20, 21, 23, 24, 25, 26, 28.
- Positive mood items are: 2, 8, 12, 17, 27, 30.
- Transcendence items are: 1, 7, 11, 13, 19, 22.
- Ineffability items are: 3, 10, 29.

The MEQ30-total score is computed by taking the mean response to all items.

3 Ego Dissolution Inventory (EDI)

3.1 Introduction

The Ego Dissolution Inventory (EDI) is an self-completed questionnaire designed to measure ego-dissolution.

3.2 Analysis and reporting

The EDI consists of 8 visual analogue scale items and a mean score on all 8 items is calculated for a single EDI factor.

4 Timeline Follow-Back (TLFB)

4.1 Introduction

Timeline Follow-back (TLFB) is a calendar-based method used to estimate an individual's daily drinking habits over a given time period.

4.2 Analysis and reporting

The following will be calculated:

Scoring item	Calculation
Longest continuous number of abstinence (days)	Max number of continuous days where units=0
Maximum number of standard units of alcohol consumed on any one day	Max units where units >0
Number of Heavy Drinking Days (HDD)	Total days where units >=9 for men; Total days where units >=7 for women
Percentage of Heavy Drinking Days (PHDD) in 85d prior D-3 (or start of detox) vs PHDD post-dosing measured on d14, d28, d56, d84	% of the number of HDD (see above for definition) for 85d prior D-3 (or start of detox) vs % of the number of HDD D0-D14, D0-D28, D0-D56, D0-D84
Percentage of drinking days (PDD) in 85d prior D-3 (or start of detox) vs PDD post-dosing measured on d14, d28, d56, d84	% of the total days where units > 0 for 85d prior D-3 (or start of detox) vs % of the total days where units > 0 on D0-D14, D0-D28, D0-D56, D0-D84
Mean Units per day (UPD): In 85d prior D-3 (or start of detox) vs UPD post-dosing measured on d14, d28, d56, d84.	(sum of all units)/(85d prior to D-3) vs (sum of all units)/(D0-D14); (sum of all units)/(D0-D28); (sum of all units)/(D0-D56); (sum of all units)/(D0-D84)

Abstinence: Percentage of Abstinent days (PAD) in 85d prior D-3 (or start of detox) vs PAD on d14, d28, d56, d84	% of days where units=0 for 85d prior D-3 (or start of detox) vs % of days where units=0 on D0-D14, D0-D28, D0-D56, D0-D84
Number of days after BPL-003 dosing to first drink	Number of days until units >0 after D0 (dosing)
Number of days after BPL-003 dosing to first HDD (defined by UK government as ≥ 7 units a day for a woman and ≥ 9 units per day for a man)	Number of days until units ≥ 9 (male) or ≥ 7 (female) after D0 (dosing)
Average number of standard units of alcohol consumed per week in 85d prior D-3 (or start of detox) vs post-dosing measured on d14, d28, d56, d84 (and reported referencing UK risk levels)	Average number of standard units of alcohol consumed per week in 85d prior D-3 (or start of detox) vs post-dosing measured on d14, d28, d56, d84

5 Alcohol Craving Questionnaire (ACQ)

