According to The National Institute for Health and Care Excellence (NICE) guidelines, treatment for AUD includes brief interventions to facilitate more healthy behaviours; specialised treatment like motivational enhancement therapy to address ambivalence about changing their drinking behaviour or dealing with their problems; detoxification to address withdrawal symptoms; cognitive-behavioural therapies to avoid relapses; and several drugs to diminish cravings or discourage relapses (National Institute for Health and Care Excellence, 2019). For people with severe alcohol dependence and/or significant physical or psychiatric comorbidity, this may require medication-assisted alcohol withdrawal in an inpatient or residential setting (Specialist Clinical Addiction Network, 2006). Current United States (US) Food and Drug Administration (FDA)-approved pharmacological treatments include acamprosate, naltrexone, and disulfiram. Scientific evidence demonstrates the benefits of combining approved drugs for treating AUD with evidence-based behavioural therapy, and the outcomes are generally better when medication and therapy are combined (Mason, 2021). Other emerging and off-label pharmacotherapies include nalmefene, which was approved in Europe and Australia for the purpose of controlling drinking, baclofen, topiramate, and gabapentin (Morley, 2021).

Peer-support group counselling is an approach used to facilitate relapse prevention. Alcoholics Anonymous is one of the earliest organizations formed to provide peer support and it is still the largest; other organisations exist for those who do not agree with the Alcoholics Anonymous philosophy (Kelly, 2020). Yet, despite all the harms and a variety of treatment options, only 19.8% of individuals with lifetime prevalence of AUD have sought treatment (Grant, 2015). Most studies examining the outcomes of people attending alcohol treatment find that 70% to 80% will relapse in the year following treatment, with the highest rate of relapse taking place in the first 3 months after completing treatment (Schuckit, 2009). Poor treatment response is typically associated with greater baseline alcohol use severity indicators (Davis, 2018a; Saitz, 2010), suggesting an unmet intervention need in heavy users.

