3.3. Exploratory Endpoints

Pharmacokinetic:

- Blood samples to determine 5-MeO-DMT and its metabolites (including bufotenine) plasma concentrations will be taken after dosing on Day 0.

Drinking Craving:

- Change in alcohol craving as measured by Alcohol Craving Questionnaire (ACQ) at Days 1, 7, 28, 56, and 84 compared to Baseline (pre-dose on Day 0)
- Alcohol cravings as measured by Craving Visual Analogue Scale (VAS)
- Alcohol withdrawal symptoms as measured by Clinical Institute Withdrawal Assessment (CIWA-Ar)
- Consequences of alcohol use as measured by Short Inventory of Problems (SIP)

Alcohol Use:

Using the Timeline Follow-Back (TLFB) interview, the following parameters of alcohol use in the 90 days before dosing and endpoint will be recorded:

- Percentage of Heavy Drinking Days (PHDD) in 85d prior D-3 (or start of detox) vs PHDD post-dosing measured on d14, d28, d56, d84.
- Percentage of drinking days (PDD) in 85d prior D-3 (or start of detox) vs PDD post-dosing measured on d14, d28, d56, d84.
- Mean Units per day (UPD): In 85d prior D-3 (or start of detox) vs UPD post-dosing measured on d14, d28, d56, d84.
- Abstinence: Percentage of Abstinent days (PAD) in 85d prior D-3 (or start of detox) vs PAD on d14, d28, d56, d84 (with biomarker verification).
- Longest duration (days) of continuous abstinence
- Number of days after BPL-003 dosing to first drink
- Number of days after BPL-003 dosing to first HDD (defined by UK government as >7 units a day for a woman and >9 units per day for a man)
- Average number of standard units of alcohol consumed per week in 85d prior D-3 (or start of detox) vs post-dosing measured on d14, d28, d56, d84 (and reported referencing UK risk levels)
- Maximum number of standard units of alcohol consumed on any one day

Correlation of PD effects with alcohol use and related symptoms

The correlation of the occurrence of a “complete mystical experience” and “ego dissolution”, measured by the MEQ30 and EDI, with improvement in alcohol use and craving (measured by AQC, TLFB, EtG, CDT)

Biomarkers

- Alcohol use as measured by EtG in urine at Days 1, 28, 56, 84 compared to Screening
- Alcohol use as measured by CDT in blood at Days 28 & 84 compared to Screening

Wellbeing

- Change in Montgomery–Asberg Depression Rating Scale (MADRS) at Days 28, 56, and 84 compared to Baseline
- Change in Clinical Global Impression Severity (CGIS) at Days 1, 28, 56, and 84 compared to Baseline

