15.1 Pharmacokinetic concentration data

Plasma concentrations of 5-MeO-DMT and its metabolites (bufotenine, 5-methoxyindolacetic acid (5-MIAA) and 5-MeO-DMT-N-Oxide) will be listed and summarised by treatment.

Using actual sample times, linear and semi-logarithmic concentration-time plots of each patient will be prepared. The same linear and logarithmic scales will be used for each patient. The linear and semi logarithmic plots for a given patient will be presented on the same page. For clarity in presentation, individual profiles for different analytes will be separate.

Nominal blood sampling times will be used to calculate the mean (SD) drug concentrations at each time point. Comparative linear and semi logarithmic plots of the mean (\pm SD) concentration-time data for each group will be prepared.

For individual concentration–time plots, plasma concentrations below the limit of quantification of the assay (BLQ) will be treated as follows: values that occur before t_{max} will be taken as zero; all other values will be taken as missing.

For calculation of plasma concentration summary statistics, BLQ values will be taken as zero, unless they fall between two quantifiable concentrations, in which case they will be treated as missing.

16 Pharmacodynamic analyses

PD data will be summarised using the ITT and PP (alcohol use from the TLFB interview, and MEQ only) Population.

PD data will be listed by treatment and time point and summarised by treatment and time point. Changes from baseline questionnaires will be summarised by time point and treatment.

The PD data includes the following psychometric scales and questionnaires: Stanford Expectation of Treatment Scale (SETS), Mystical Experience Questionnaire (MEQ-30), Ego Dissolution Inventory (EDI), 5-Level EuroQol 5-Dimension (EQ-5D-5L), Timeline Follow-Back (TLFB), Montgomery-Åsberg Depression Rating Scale (MADRS), Alcohol Craving Questionnaire (ACQ), Craving Visual Analogue Scale (VAS), Clinical Global Impression of Severity (CGI-S), Patient Global Impression of Change (PGIC), Clinical Institute Withdrawal Assessment for Alcohol-Revised (CIWA-Ar), Short Inventory of Problems (SIP).

Each psychometric scale/questionnaire will be reported using standard scales as described in Appendix A: Pharmacodynamic analysis.

The scales will be listed and summarised.

In addition, an individual plot of the mean units of alcohol per day (UPD) from the TLFB questionnaire will be produced.

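### The Day 84 drinking rates are averages from Day 0 but are labelled by day, so a late return to baseline drinking is diluted and no planned summary shows Weeks 9 to 12 alone

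*SAP*

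**What the plan says.** Protocol Section 3.3 lists the alcohol-use rates as a comparison of the 85 days before Day -3 (or the start of detox) with a post-dose value, for example "vs PHDD post-dosing measured on d14, d28, d56, d84". It names days and gives no window.

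SAP Appendix A, Section 4.2 supplies the windows:

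- PHDD: "vs % of the number of HDD D0-D14, D0-D28, D0-D56, D0-D84".
- PDD: "of the total days where units > 0 on D0-D14, D0-D28, D0-D56, D0-D84".
- UPD: "sum of all units)/(D0-D14); (sum of all units)/(D0-D28); (sum of all units)/(D0-D56); (sum of all units)/(D0-D84".
- PAD: "of days where units=0 on D0-D14, D0-D28, D0-D56, D0-D84".

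For weekly units the calculation cell only restates the endpoint, "Average number of standard units of alcohol consumed per week in 85d prior D-3 (or start of detox) vs post-dosing measured on d14, d28", and sets no post-dose window. The count of heavy drinking days (HDD) and the maximum daily units have none either.

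The table shell T_PD1a and the listing shell L_PD6_PG head the columns or rows with the 85-day baseline and then Day 14, Day 28, Day 56 and Day 84. Neither carries a note that the values accumulate from Day 0. SAP Section 16 adds that "an individual plot of the mean units of alcohol per day (UPD) from the TLFB questionnaire will be produced". The contents table in SAP Section 19.1 names Listing 16.2.6.6 as the source of that plot (Figures 14.2.5.1 and 14.2.5.2), and that listing's shell holds only the baseline and the four cumulative values.

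**The concern.** Someone reading a table row labelled Day 84 will take it as drinking at about Day 84, particularly as the protocol describes the value as measured on that day. It is in fact the mean over the whole follow-up, and each later value contains all the earlier ones.

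The exploratory objective is the effect of one dose plus relapse prevention psychotherapy on alcohol use, with 12 weeks of follow-up. The main alternative to a lasting effect is one that fades. Cumulative averages carry early improvement into every later row, so the two patterns look more alike than they are. The time to first drink and the time to first HDD date the start of a lapse but do not say whether heavy drinking then continued.

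**Working it through.** The plan states no figure to reproduce: there is no sample size calculation and no hypothesis test. The check is day-count arithmetic.

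**Inputs.** Windows from SAP Appendix A, Section 4.2, counted inclusively: D0-D14 = 15 days, D0-D28 = 29, D0-D56 = 57, D0-D84 = 85. The last 28 days are D57-D84. The baseline window is 85 days.

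**Overlap.** 57/85 = 67% of the Day 84 window is the Day 56 window.

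**Formula.** Let b be the baseline rate, e the rate on D1-D56 and l the rate on D57-D84, with no drinking assumed on D0 itself. Then

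Day 84 value = (56e + 28l)/85.

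For full relapse set l = b. The true change in Weeks 9 to 12 is then zero, and the relative change in the Day 84 value does not depend on b. The last column repeats the sum with D0 left out (84 days).

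| e as share of b | Day 84 value / b | Change, D0 counted | Change, D0 not counted |
|---|---|---|---|
| 0% | 28/85 = 0.329 | -67.1% | -66.7% |
| 25% | (14 + 28)/85 = 0.494 | -50.6% | -50.0% |
| 50% | (28 + 28)/85 = 0.659 | -34.1% | -33.3% |
| 75% | (42 + 28)/85 = 0.824 | -17.6% | -16.7% |
| 100% | 84/85 = 0.988 | -1.2% | 0% |

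**Example (assumed baseline PHDD 50%).** No heavy days to Day 56, then 50% of the last 28 days, which is 14 heavy days. Day 84 PHDD = 14/85 = 16.5%, a change of 16.5 - 50 = -33.5 points, against 0 points in Weeks 9 to 12. If all of the last 28 days are heavy, Day 84 PHDD = 28/85 = 32.9%, a change of -17.1 points, against +50 points in Weeks 9 to 12.

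**PAD.** PAD is 100% minus PDD, so its point change is the mirror image: with baseline PDD 50% and the first pattern applied to drinking days, PAD rises from 50% to 83.5% (+33.5 points).

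**Break-even.** After abstinent Weeks 1 to 8, the Day 84 value equals baseline only if l = (85/28)b = 3.04b. For a percentage of days that is impossible once b exceeds 28/85, about 33%.

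**What can be recovered.** Late rate = (85 x Day 84 value - 57 x Day 56 value)/28. In the first example this is (85 x 16.47% - 57 x 0%)/28 = 50%, the true figure.

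**HDD count.** If the D0-based windows also apply to the count, which the SAP does not say, unchanged drinking at 40% heavy days gives 0.40 x 85 = 34 at baseline and 0.40 x 15 = 6 at Day 14.

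**The case against.** The cumulative choice is coherent. D0-D84 is 85 days, the same length as the baseline, so it is a fair overall comparison. The endpoints are exploratory, nothing is tested, and there are at most 12 patients, so individual listings and plots will carry much of the weight.

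A late relapse also leaves a trace. L_PD6_PG prints the four values side by side, and the UPD line would rise from Day 56 to Day 84. A patient with 28 heavy days before Day 56 and one with 28 heavy days after it both show 32.9% at Day 84, but at Day 56 the first shows 28/57 = 49.1% and the second 0%. Complete data listings are planned. Urine EtG and the craving questionnaire are taken at Days 56 and 84, and CDT at Days 28 and 84.

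Most of this stands, and it limits the point to dilution. A reader might infer that these windows hide a relapse or cannot tell a fading effect from a lasting one. The documents do not support that, because the sequence of values differs and the late rate can be worked out.

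The remedies are partial, though. Back-calculation needs complete daily records, and SAP Section 12.1 says missing data are not imputed. It works on summary means only if the same patients contribute to both windows, and not at all on medians, SDs, minima or maxima. Protocol Section 9.17.1 puts EtG detection at up to about 72 hours. CDT is a useful late signal but not a drinking rate. Raw listings are not a summary.

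**Conclusion.** The point holds for PHDD, PDD, UPD and PAD. Their Day 84 values are 12-week averages labelled as a day, and no planned table, listing or plot of the timeline follow-back (TLFB) data gives a Weeks 9 to 12 rate. With full relapse in Weeks 9 to 12, the reported Day 84 change in PHDD, PDD or UPD is about -67% after abstinent Weeks 1 to 8 and about -34% if Weeks 1 to 8 ran at half of baseline. These sizes assume no drinking on Day 0 and complete records. They also depend on early improvement: with none, the distortion is about -1% or nil.

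Four stronger readings are not supported:

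- **Every post-dose drinking measure is cumulative.** Weekly units, the HDD count and maximum units have no stated window, which is a separate gap.
- **A relapsed patient is classed as improved.** The SAP has no such category for drinking; it reports change from baseline.
- **The count and the maximum will show false falls from baseline.** T_PD1a plans no change from baseline for either, and a patient who keeps reaching the same peak has the same maximum in any window.
- **The protocol places peak relapse inside this follow-up.** Protocol Section 1.1 says "with the highest rate of relapse taking place in the first 3 months after completing treatment", whereas relapse prevention sessions here run to Week 12.

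Severity is modest because the endpoints are exploratory and descriptive. The change is still worth making because it is cheap and bears on whether the effect lasts.

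**What to change.** In SAP Appendix A, Section 4.2, T_PD1a, L_PD6_PG and Figures 14.2.5.1 and 14.2.5.2:

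1. Add non-overlapping windows D0-D14, D15-D28, D29-D56 and D57-D84 for PHDD, PDD, UPD and PAD, with change from baseline for each.
2. Keep the D0-based rows, including D0-D84 as the comparison that matches the baseline in length, and label them *cumulative from Day 0*.
3. Apply the same interval windows to average weekly units and state them.
4. As a minor point, if the HDD count stays beside the 85-day baseline, state its window and scale it to a common length, or rely on PHDD.

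The cost is SAP wording and shell programming. TLFB is already taken weekly to Day 84 with each day recorded, so nothing new is collected. The drawback is that shorter windows give slightly noisier individual values.

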 - **Relapse prevention psychotherapy:** Patients will have weekly sessions following the dose of BPL-003 as defined in the AUD Therapy Manual (can be either face to face or remote) with an AUD therapist.

Number of patients (planned):

Enrolment of patients with AUD is planned until up to 12 evaluable patients in up to 2 Cohorts have been dosed and completed Day 0 of the study. Although this study is exploratory and there is no formal sample size calculation, the sample size is estimated to be able to detect common drug-induced safety events in this patient population.

Diagnosis and main criteria for inclusion:

To be eligible to participate in this study, patients must meet the following criteria:

Inclusion Criteria:

1. Willing and able to give informed consent
2. Age 18 to 64 years at Screening
3. Diagnosed with moderate to severe AUD (based on Diagnostic and Statistical Manual of Mental Disorders, Fifth Edition [DSM-5])
4. Minimum of 4 heavy drinking days (HDD) in the 28 days before Screening
5. No more than 14 days have elapsed since the last HDD or completion of detoxification (at point of screening), with no HDD in the 72 hours prior to dosing, and no alcohol at all in the 24 hours prior to dosing
6. Willing to abstain from using recreational drugs from Screening until end of the study
7. Willing to abstain from smoking during their time in the clinic on the day of drug administration as instructed by clinical staff
8. Willing to refrain from psychedelic drug use (excluding the study drug) from Screening until the end of the study
9. Able (in the Investigator's opinion) and willing to undertake and comply with all study requirements, with the ability to complete all protocol-required assessment tools and to comply with all study visits

10. Willing to allow their own general practitioner, and consultant if appropriate, to be informed of study participation
11. Living in stable/secure accommodation in the community
12. In possession of a personal mobile phone and able to nominate at least one locator individual (e.g., a family member, friend, or recovery mentor), with a verifiable address and a telephone number to assist with the arrangement of follow-up appointments

Exclusion Criteria:

General Medical Exclusion Criteria:

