Health Status and QoL																		
EQ-5D-5L	X									X								X
Treatment Model Feedback ²²											X							
Adverse Events																		
Adverse events	X	X	X	X	X	X	X	X	X	X	X	X	X	X	X	X	X	X
Reactivation Questionnaire							X			X								X

Abbreviations: ACQ = Alcohol Craving Questionnaire; AE = adverse event; ALT = alanine aminotransferase; AST = aspartate aminotransferase; AUD = alcohol use disorder; BP = blood pressure; CDT = carbohydrate deficient transferrin; CGIS = Clinical Global Impression of Severity; CIWA-Ar = Clinical Institute Withdrawal Assessment-Alcohol revised; C-SSRS = Columbia-Suicide Severity Rating Scale; ECG = electrocardiogram; EDI = Ego Dissolution Inventory; EQ-5D-5L = 5-level EuroQol-5 Dimension; EtG = ethylglucuronide; FSH = follicle-stimulating hormone; GGT = gamma-glutamyl transpeptidase; HR = heart rate; MADRS SIGMA = Montgomery–Asberg Depression Rating Scale, SIGMA version; MCV = mean corpuscular volume; MEQ30 = Mystical Experience Questionnaire; MINI = Mini-International Neuropsychiatric Interview; PGIC = Patient Global Impression of Change; PK = pharmacokinetics; QoL = quality of life;; SETS = Stanford Expectation of Treatment Scale; SIP = Short Inventory of Problems; TLFB = Timeline Follow-Back.

Notes:

1. Screening will occur from Day -28. The maximum time to complete Screening and Psychedelic Preparation will be 28 days.
2. The Psychedelic Preparation sessions may be completed in less than 12 days if the therapist has a good rapport with the patient, with a window of +/-5 days for Day -12 & Day -7, however they should not fall on the same day. The final preparation visit has a window of +2 days and should be Day -3 to Day -1 only. It is preferable that visits be face to face, but if necessary, visits can be completed remotely with the exception of Screening, Day -3, Day 0, Day 1, Day 28, Day 56, Day 84.
3. Unless otherwise indicated, ALL assessments, testing, and blood samples for haematology and clinical chemistry are to be performed PRIOR to dosing.

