4.2.3 Exploratory endpoint(s)

Pharmacokinetic:

- Blood samples to determine 5-MeO-DMT and its metabolites (including bufotenine) plasma concentrations will be taken after dosing on Day 0.

Drinking Cravings and withdrawal:

- Change in alcohol craving as measured by Alcohol Craving Questionnaire (ACQ) at Days 1, 7, 28, 56, and 84 compared to Baseline (pre-dose Day 0)
- Alcohol cravings as measured by Craving Visual Analogue Scale (VAS)
- Alcohol withdrawal symptoms as measured by Clinical Institute Withdrawal Assessment (CIWA-Ar)

Alcohol Use:

- Using the Timeline Follow-Back (TLFB) interview, the following parameters of alcohol use in the 90 days before dosing and endpoint will be recorded:
 - Longest duration (days) of continuous abstinence
 - Maximum number of standard units of alcohol consumed on any one day
 - Number of Heavy Drinking Days (HDD)
 - Percentage of Heavy Drinking Days (PHDD) in 85d prior D-3 (or start of detox) vs PHDD post-dosing measured on d14, d28, d56, d84
 - Percentage of drinking days (PDD) in 85d prior D-3 (or start of detox) vs PDD post-dosing measured on d14, d28, d56, d84.
 - Mean Units per day (UPD): In 85d prior D-3 (or start of detox) vs UPD post-dosing measured on d14, d28, d56, d84.
 - Abstinence: Percentage of Abstinent days (PAD) in 85d prior D-3 (or start of detox) vs PAD on d14, d28, d56, d84 (with biomarker verification).
 - Number of days after BPL-003 dosing to first drink
 - Number of days after BPL-003 dosing to first HDD (defined by UK government as ≥ 7 units a day for a woman and ≥ 9 units per day for a man)
 - Average number of standard units of alcohol consumed per week in 85d prior D-3 (or start of detox) vs post-dosing measured on d14, d28, d56, d84 (and reported referencing UK risk levels)
- Consequences of alcohol use as measured by Short Inventory of Problems (SIP)
- Biomarkers:
 - Alcohol use as measured by Ethylglucuronide (EtG) in urine at Days 1, 28, 56, 84 compared to Screening
 - Alcohol use as measured by carbohydrate deficient transferrin (CDT) in blood at Days 28 & 84 compared to Screening

Pharmacodynamic

- The correlation of the occurrence of a “complete mystical experience” and “ego dissolution”, measured by the MEQ-30 and EDI, with improvement in alcohol use and craving (measured by ACQ, TLFB, EtG, CDT)

Wellbeing:

- Change in Montgomery–Asberg Depression Rating Scale (MADRS) at Days 28, 56, and 84 compared to Baseline

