Source: Listing 16.2.xx

Programming notes: For EDI and visual analogue scale, the first column will be "Score (mm)". Include all subscales as stated in appendix A

Template T_PD1a

Table 14.2.2.xx Summary of Timeline Follow-Back (TLFB) [intent-to-treat population]

Scoring Item	Treatment	Planned Relative Time	n	Mean	SD	Median	Min	Max	Change from Baseline					
									n	Mean	SD	Median	Min	Max
Longest continuous number of abstinence (days)	Treatment 1 (N=xx)		x	x.x	x.xx	x.x	x	x						
Max number of standard units of alcohol consumed on any one day	Treatment 1 (N=xx)	85 Days Prior Day-3	x	x.x	x.xx	x.x	x	x						
		Day 14	x	x.x	x.xx	x.x	x	x						
		Day 28	x	x.x	x.xx	x.x	x	x						
		Day 56	x	x.x	x.xx	x.x	x	x						
		Day 84	x	x.x	x.xx	x.x	x	x						
Number of Heavy Drinking Days (HDD)	Treatment 1 (N=xx)	85 Days Prior Day-3	x	x.x	x.xx	x.x	x	x						
		Day 14	x	x.x	x.xx	x.x	x	x						
		Day 28	x	x.x	x.xx	x.x	x	x						
		Day 56	x	x.x	x.xx	x.x	x	x						
		Day 84	x	x.x	x.xx	x.x	x	x						
Number of days after dosing to first drink	Treatment 1 (N=xx)		x	x.x	x.xx	x.x	x	x						
Number of days after dosing to first HDD	Treatment 1 (N=xx)		x	x.x	x.xx	x.x	x	x						
Average number of standard units of alcohol consumed per week	Treatment 1 (N=xx)	85 Days Prior Day-3	x	x.x	x.xx	x.x	x	x						
		Day 14	x	x.x	x.xx	x.x	x	x	x	x.x	x.xx	x.x	x	x
		Day 28	x	x.x	x.xx	x.x	x	x	x	x.x	x.xx	x.x	x	x
		Day 56	x	x.x	x.xx	x.x	x	x	x	x.x	x.xx	x.x	x	x
		Day 84	x	x.x	x.xx	x.x	x	x	x	x.x	x.xx	x.x	x	x
Percentage of Heavy Drinking Days (PHDD)	Treatment 1 (N=xx)	85 Days Prior Day-3	x	x.x	x.xx	x.x	x	x						
		Day 14	x	x.x	x.xx	x.x	x	x	x	x.x	x.xx	x.x	x	x
		Day 28	x	x.x	x.xx	x.x	x	x	x	x.x	x.xx	x.x	x	x
		Day 56	x	x.x	x.xx	x.x	x	x	x	x.x	x.xx	x.x	x	x
		Day 84	x	x.x	x.xx	x.x	x	x	x	x.x	x.xx	x.x	x	x
Percentage of Drinking Days (PDD)	Treatment 1 (N=xx)		x	x.x	x.xx	x.x	x	x	x	x.x	x.xx	x.x	x	x
Mean Units per Day (UPD)	Treatment 1 (N=xx)		x	x.x	x.xx	x.x	x	x	x	x.x	x.xx	x.x	x	x

Abstinence: Percentage of Treatment 1 (N=xx) x x.x x.xx x.x x x x x.x x.xx x.x x x

Abstinent Days (PAD)

Source: Listing 16.2.xx

Note: 85 Days Prior Day -3 = 85 Days Prior Day -3 (or start of detox)

Programming notes: Continued with all the timepoints (85 Days Prior Day-3, Day 14, Day 28, Day 56 and Day 84) for PDD, UPD and PAD

Template T_PD2

Table 14.2.2.xx Summary of Montgomery-Åsberg Depression Rating Scale (MADRS) [intent-to-treat population]

Question	Treatment	Planned Relative Time	n	Mean	SD	Median	Min	Max	Change from Baseline					

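### The UPD baseline calculation omits the start-of-detox anchor that its own label keeps, and the SAP gives no denominator for detoxified patients whose 85-day window cannot be filled

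*SAP*

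**What the plan says.** SAP Appendix A 4.2 has a label column and a calculation column for each TLFB measure. For UPD the two differ.

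- Label: "Mean Units per day (UPD): In 85d prior D-3 (or start of detox) vs UPD post-dosing measured on d14, d28, d56, d84".
- Calculation: "sum of all units)/(85d prior to D-3". The detox alternative is missing.

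The neighbouring calculations keep it. Percentage of heavy drinking days (PHDD) is taken as a percentage "of the number of HDD (see above for definition) for 85d prior D-3 (or start of detox", and percentage of drinking days (PDD) as a percentage "of the total days where units > 0 for 85d prior D-3 (or start of detox". Percentage of abstinent days (PAD) and weekly units follow the same pattern. The footnote to the TLFB table shell (T_PD1a), which covers UPD, reads "Note: 85 Days Prior Day -3 = 85 Days Prior Day -3 (or start of detox", and the listing shell (L_PD6_PG) repeats it. SAP section 17, on changes from the protocol analysis, mentions no change to UPD.

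On data collection, SAP 4.2.3 says that "the following parameters of alcohol use in the 90 days before dosing and endpoint will be recorded". On eligibility, Inclusion criterion 5 in the Protocol Synopsis reads "No more than 14 days have elapsed since the last HDD or completion of detoxification (at point of screening", so a patient may enter after a detox already completed. Note 1 to the Protocol's Schedule of Events says "Screening will occur from Day -28. The maximum time to complete Screening and Psychedelic Preparation will be 28 days", and the table puts Screening at Day -28 to Day -14.

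SAP 12.1 rules out imputation. No section says which denominator applies when part of the baseline window was not recorded.

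**The concern.** There are two problems, and both concern patients detoxified before Screening.

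First, a programmer works from the calculation column. Coded literally, baseline UPD covers the 85 days before D-3 for everyone. For a detoxified patient that span includes the detox and the days after it, which the other measures leave out. If the patient drank less in those days, baseline UPD is too low and the change from baseline too small. UPD and weekly units would then describe different periods for the same person in the same table. UPD is also the only TLFB measure with its own figures (individual plots, ITT and PP).

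Second, the 85-day window was sized for patients indexed at D-3. Anchored at the start of detox, it either reaches back beyond the recorded days or, if it is only cut short, holds fewer than 85 days. Without a stated denominator, a programmer may divide by 85 in both cases.

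With at most 12 patients, one detoxified patient carries at least 1/12 (8%) of the weight in a mean change.

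**Working it through.** **Inputs.** Recorded pre-dose days: D-90 to D-1 (SAP 4.2.3). Window length: 85 days (SAP Appendix A 4.2). Screening: D-28 to D-14 (Schedule of Events). Detox completed 0 to 14 days before Screening (Inclusion criterion 5). At least 4 heavy drinking days in the 28 days before Screening (Inclusion criterion 4), so detox is taken to start no more than 24 days before Screening. Detox length is not in the documents; 5 to 10 days is assumed.

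**The plan's own window, no detox.** The 85 days before D-3 are D-88 to D-4. All lie within D-90 to D-1, with 2 days to spare at the early end. D0 to D84 inclusive is also 85 days. The design is coherent for these patients.

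**Range of detox start, s.** Latest: Screening D-14, no gap, 5-day detox, s = D-19. Earliest: Screening D-28, 14-day gap, 10-day detox, s = D-52, which is also the limit set by the 24-day bound.

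**Reading A: the 85 days are counted back from s.** The window is s-85 to s-1. Days outside the recorded period = max(0, -5 - s), so the window is full only if s is D-5 or later.

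- s = D-19: 14 outside (14/85 = 16%), 71 recorded.
- s = D-35: 30 outside (35%), 55 recorded.
- s = D-52: 47 outside (55%), 38 recorded.

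The gap does not depend on the assumed length. Detox complete by Screening means s is D-14 at the latest, which already leaves 9 of 85 days unrecorded. Over all combinations of Screening day and gap, equally weighted, the average outside is 28, 30 and 33 days for a 5-, 7- and 10-day detox (33%, 35%, 39%).

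**Reading B: the D-88 window is cut off at s.** Days left = 88 + s, which is 69 at s = D-19 and 36 at s = D-52. None falls outside the 90, but the window no longer has 85 days.

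**Literal UPD cell.** With no drinking after s, baseline UPD as a fraction of the pre-detox level = (88 + s)/85.

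- s = D-19: 69/85 = 81%.
- s = D-35: 53/85 = 62%.
- s = D-52: 36/85 = 42%.

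**Illustration** (assumed 20 units/day before detox, 0 after, s = D-35):

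| Rule | Baseline UPD |
|---|---|
| Literal cell | 20 × 53/85 = 12.5 |
| Reading A, divided by 85 | 20 × 55/85 = 12.9 |
| Reading B, divided by 85 | 20 × 53/85 = 12.5 |
| Reading A or B, divided by recorded days | 20 |

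Weekly units, anchored at detox and averaged over recorded days, would be 20 × 7 = 140, against 7 × 12.5, about 87, implied by the literal UPD.

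**The case against.** The best defence is that the UPD omission sits in a single cell. The row label, the endpoint lists in both documents and both shell footnotes resolve it the same way. That is right: a reader might infer that UPD was deliberately given a different baseline, and the documents do not support that. What remains is a contradiction in the column that will be coded.

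Three further inferences go too far.

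- *Most of the detox-anchored window is missing.* More than half is unrecorded only if detox began on or before D-48: 0, 3 and 15 of 225 combinations for a 5-, 7- and 10-day detox. Usually most of the window is covered.
- *All baselines are understated.* For PHDD, PDD and weekly units this happens only if 85 stays the denominator. SAP 9.1 and 12.1 (observed data, no imputation) lean towards recorded days, though neither says so for TLFB. PAD would fall under a fixed 85 only if unrecorded days are not counted as abstinent; averaging in abstinent post-detox days would raise it.
- *A relapse would read as an increase.* With 20 units/day before detox, none after it until dosing and 10 after dosing, the literal cell gives that result only if detox began on or before D-46: 3, 10 and 28 of 225 combinations (1%, 4%, 12%). It is a corner case.

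It can also be said that 90 days may not be a hard limit, since neither Protocol 9.5 nor the schedule states the recall length at Screening. More days may therefore exist than the endpoint definition promises. Dividing by recorded days handles that too.

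Finally, these are exploratory endpoints with no hypotheses, and the documents do not say that any patient was detoxified; criterion 5 equally admits patients by their last heavy drinking day. This limits the impact but does not settle the rule.

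**Conclusion.** The point holds in two parts. The UPD calculation contradicts its label, the endpoint list, the shell footnotes and the other baseline calculations. If coded literally, it understates baseline UPD for a patient detoxified before Screening whenever drinking fell after detox began. The size is 42–81% of the pre-detox level, assuming a 5–10 day detox and no later drinking.

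The SAP also does not say whether the start of detox moves the 85-day window or shortens it, or what to divide by. On the same assumed length, moving it leaves 14–47 days (16–55%) unrecorded, and shortening it leaves 36–69 days. Under either reading a fixed 85 would bias PHDD, PDD, UPD and weekly units low, and PAD as well if unrecorded days are not counted as abstinent.

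Patients without detox are unaffected, and no primary or secondary endpoint is touched. It is worth correcting because the rule as written can give a wrong number and the correction is nearly free.

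**What to change.** Amend SAP Appendix A 4.2 before database lock:

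1. Add the start-of-detox alternative to the UPD calculation cell.
2. Define one index date per patient (start of detox if there was one, otherwise D-3) and one window, stating whether detox moves or shortens it. Apply both to PHDD, PDD, PAD, UPD and weekly units.
3. Divide by the days actually recorded in that window, not by 85.
4. Report the number of recorded pre-detox days for each detoxified patient. The raw count of heavy drinking days, shown in the table shell under the 85-day heading, also needs this number to be interpretable.

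The cost is SAP wording and a small programming change. The downside is that detoxified patients' baselines rest on fewer days, which item 4 makes visible. Asking for longer recall at Screening is optional. It would change the Protocol's 90-day collection and help only patients not yet screened. The Protocol's change summary moved the last patient visit to September 2024, and the SAP cites the Protocol version of 29 August 2024, so it is probably too late.
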